INR	International normalized ratio
METC	Medical research ethics committee (MREC); in Dutch: medisch ethische
	toetsing commissie (METC)
MGP	Matrix Gla Protein
pDES	Plasma Desmosine
SAE	Serious Adverse Event
SD	Standard deviation
SNP	Single nucleotide polymorphism
Sponsor	The sponsor is the party that commissions the organisation or
	performance of the research, for example a pharmaceutical
	company, academic hospital, scientific organisation or investigator. A
	party that provides funding for a study but does not commission it is not
	regarded as the sponsor, but referred to as a subsidising party.
SUSAR	Suspected Unexpected Serious Adverse Reaction
VKA	Vitamin K antagonist
VKORC1	Vitamin K 2,3-epoxide reductase complex 1
WBP	Personal Data Protection Act (in Dutch: Wet Bescherming
	Persoonsgevens)
WMO	Medical Research Involving Human Subjects Act (in Dutch: Wet
	Medisch-wetenschappelijk Onderzoek met Mensen

SUMMARY

Rationale:

Elastin is a unique protein providing elasticity, resilience and deformability to dynamic tissues, such as lungs and vasculature. Elastin fibers are characterized by their high affinity for calcium. However, calcified elastin is more prone to the degrading effects of proteases and, in turn, partially degraded elastin has an even higher affinity for calcium. A disturbed balance between proteases and anti-proteases is a major underlying mechanism in the development of chronic obstructive pulmonary disease (COPD). Virtually the only protein that can protect elastin from calcification is matrix Gla-protein (MGP), which needs vitamin K for its activation. In COPD patients, a lower vitamin K status is found when compared to control subjects and an inverse association exists between vitamin K status and elastin degradation. In addition, vitamin K status is lower and elastin degradation is accelerated in Vitamin K antagonist (VKA) users.

VKAs are widely used. Nowadays, an increasing number of patients uses direct oral anticoagulants (DOACs), which do not influence vitamin K status. We hypothesize that discontinuation of VKAs results in an improved vitamin K status and deceleration of elastin degradation. In order to test this hypothesis, we want to conduct an observational pilot study in which the change in elastin degradation– quantified by plasma desmosine concentrations – in patients who discontinue use of VKAs will be used as primary endpoint.

Objective: To evaluate whether discontinuation of VKAs results in a higher vitamin K status and deceleration of the rate of mature cross-linked elastin degradation.

Study design: Observational study.

Study population: A total of 30 VKA users who will discontinue the use of VKAs.

Main study parameters/endpoints: The primary endpoint is the change in the rate of elastin degradation quantified by the plasma desmosine assay. Secondary endpoints are the change in vitamin K status quantified by measuring plasma levels of dephosphorylated uncarboxylated, (i.e. dp-uc, inactive) Matrix Gla Protein (MGP), the relation between desmosine and dp-ucMGP and differences of desmosine and dp-ucMGP levels among subjects with different polymorphisms of the vitamin K 2,3-epoxide reductase complex 1 (VKORC1) gene.

Nature and extent of the burden and risks associated with participation, benefit and group relatedness: We will draw extra blood collection tubes at two moments. The first time is during one of the last regular INR testing at the anticoagulation clinic, therefore no additional venipuncture has to be performed. At this moment two additional blood collection tubes will be drawn. The second moment is approximately 6 months after discontinuation of VKAs. At this point the patient will undergo an additional venipuncture. Patients are asked to

Version number: 4.0, August 2017

fill in a questionnaire concerning age, gender, length, height, indication for VKA use, duration of VKA use, smoking status and history, presence of COPD and other pulmonary disease, whether patients will switch to DOACs or will completely stop the use of anticoagulants, vitamin D supplementation, use of multivitamins and use of medications. Furthermore, we will record the INR at baseline. Participants may experience some discomfort during blood sampling. Participating in the study has negligible risks.

1. INTRODUCTION AND RATIONALE

Elastin is a unique protein providing elasticity, resilience and deformability to dynamic tissues, such as lungs and vasculature.¹ Elastin fibers are almost exclusively developed before birth and in the first period of life after which the synthesis of elastin is suppressed at a post-transcriptional level.¹ Elastin can be degraded by certain proteases, also referred to as elastases.¹ Elastin has high affinity for calcium,¹ and the calcium content of elastin fibers therefore increases during aging.² Calcium changes the conformation of elastin, which gives elastases access to elastin fibers leading to degradation.^{3,4} In turn, partially degraded elastin has a higher affinity for calcium due to increased polarity.⁴ Therefore, elastin calcification and elastin degradation are two pathologic processes that stimulate each other. When elastin is degraded, desmosine, a component of mature elastin, can be detected in the bloodstream. Since desmosine is only found in mature elastin, its plasma levels are a reflection of the rate of systemic elastin degradation.⁵

Chronic obstructive pulmonary disease (COPD) is characterized by a disturbed balance between proteases and anti-proteases, resulting in an accelerated degradation of elastin in the lungs, but also in blood vessels.⁶ Besides elastin degradation, calcification of elastin, i.e. in coronary arteries, is also accelerated in patients with COPD.⁷

Matrix Gla protein (MGP) is a potent inhibitor of elastin calcification and needs vitamin K to become activated. In an observational epidemiological study, higher vitamin K2 intake was associated with less vascular calcification.⁸ In addition, three years of vitamin K2 supplementation in postmenopausal women resulted in a decrease of arterial stiffness, while an increase was observed in the placebo group.⁹ The dephophorylated uncarboxylated (i.e. inactive) form of MGP, dp-ucMGP, can be measured in plasma and its levels are negatively associated with vitamin K status. Therefore, dp-ucMGP levels are used as a measure for vitamin K status.

Earlier, we found a reduced vitamin K status in patients with COPD compared with patients without COPD and an inverse association between vitamin K status (quantified by dp-ucMGP levels) and elastin degradation (quantified by desmosine levels) among COPD patients (abstract ATS 2016). Recently, in 106 VKA users we found higher desmosine and dp-ucMGP levels when compared with patients who do not use VKAs. In VKA users, we also found an inverse association between vitamin K status and elastin degradation (quantified by plasma dp-ucMGP and desmosine levels, respectively).

During activation of vitamin K dependent proteins such as MGP, vitamin K is oxidated from vitamin K 2,3-epoxide to vitamin K hydroquinone. Subsequently, vitamin K 2,3-epoxide needs to be recycled to the quinone form by an enzyme called vitamin K 2,3-epoxide reductase complex 1 (VKORC1). Different single nucleotide polymorphisms of this gene exist, each resulting in a different level of expression of the enzyme. Since the VKORC1 enzyme is the direct pharmacologic target of VKAs, this gene is for an important part responsible for the interindividual dose variability of VKAs. The rs9923231 SNP (g.-1639G.A) is the main genetic determinant of VKA dose requirement and can alone explain between 25% to 30% of the dose variance among patients.¹⁰

Nowadays, oral anticoagulants exist which do not influence vitamin K status, the so-called direct oral anticoagulants (DOAC). An increasingly number of patients is switching from VKAs to DOACs.

We hypothesize that discontinuation of VKAs results in an improved vitamin K status and a deceleration of elastin degradation. In order to test this hypothesis, we want to conduct an observational pilot study in which the change in elastin degradation– quantified by plasma desmosine concentrations – in patients who discontinue use of VKAs will be used as primary endpoint.

2. OBJECTIVES

We hypothesize that in persons who use VKAs, discontinuation of vitamin K antagonists leads to a deceleration of elastin degradation.

Primary Objective:

To assess the change in the rate of elastin degradation after discontinuation of vitamin K antagonists in patients who use VKAs. Quantification of the elastin degradation will be done

by measuring plasma desmosine concentrations at baseline and at 6 months after discontinuation.

Secondary Objective(s):

To evaluate the possible effects of discontinuation of VKAs on dp-ucMGP (inversely correlated with vitamin K-status).

[figure not shown]
To evaluate if different polymorphisms of the VKORC1 gene are associated with desmosine and dp-ucMGP levels and the change of both parameters after discontinuation of VKAs.

3. STUDY DESIGN

The study is designed as a non-interventional study. The follow up per patient comprises 6 months. We will include 30 VKA users who will stop the use of VKAs. At baseline, patients are asked to fill in a questionnaire and two additional samples of blood are taken during the regular testing of the international normalized ratio (INR). One blood sample is needed for determination of the VKORC1 polymorphisms and one for desmosine and dp-ucMGP levels. After 6 months, patients are asked to draw one additional blood sample for determination of desmosine and dp-ucMGP. At baseline and 6 months blood can be drawn in the Canisius Wilhelmina Hospital or one of the outposts of the anticoagulation clinic. Since the blood samples have to be stored and frozen in the laboratory in the Canisius Wilhelmina hospital within 2 hours after drawing, patients can visit the outposts within one hour before the blood samples are transported to the laboratory, i.e. within one hour before closing the outpost. If both visiting the hospital or outpost is not possible, the patient can contact the investigator to make an appointment for drawing the blood samples at home.

An overview of is given in Figure 1.

Figure 1. Overview of study and time schedule

4. STUDY POPULATION

4.1 Population (base)

We will include 30 VKA users who are going to discontinue the use of VKAs at short time

4.2 Inclusion criteria

In order to be eligible to participate in this study, a subject must meet all of the following criteria:

- Use of VKAs for at least 3 months
- Stop VKAs at short time
- Written informed consent
- Age ≥18 years
- Ability to comply with all study requirements

4.3 Exclusion criteria

A potential subject who meets any of the following criteria will be excluded from participation in this study:

- Active malignancy or cured malignancy <12 months prior to enrollment
- Use of maintenance dose oral corticosteroids
- Serious mental impairment
- Life expectation of less than 6 months on the basis of concurrent disease

4.4 Sample size calculation

It concerns a pilot study and therefore sample size calculation was not performed.

5. METHODS

5.1 Study parameters/endpoints

5.1.1 Main study parameter/endpoint

The primary endpoint is the difference in elastin degradation rate, quantified by the change in plasma desmosine levels, measured at baseline and 6 months after discontinuation of VKAs.

5.1.2 Secondary study parameters/endpoints

Secondary endpoints are:

- The difference in vitamin K status, quantified by the change in dp-ucMGP, measured at baseline and 6 months after discontinuation of VKAs.
- The association between desmosine and dp-ucMGP in patients who use VKAs and do not use VKAs.
- Differences in desmosine and dp-ucMGP levels between different VKORC polymorphisms.

5.1.3 Other study parameters

In addition, the following parameters will be registered, because of their possible confounding capacity:

- Gender
- Age
- INR
- Indication for VKA use
- Duration of VKA use
- BMI
- Smoking status and history
- Presence of COPD
- Presence of other pulmonary disease
- Medication
- Vitamin D supplementation
- Use of multivitamins
- Switch to DOACs or complete discontinuation of anticoagulant use

5.2 Study procedures

All participating subjects are asked to fill in a questionnaire at home and will be invited to visit the hospital at baseline and approximately 6 months after discontinuation of VKA use for taking blood samples. The first blood sample will be drawn during (one of) the latest regular control of their INR at the coagulation clinic, so this will not involve an extra visit or venipuncture. Patients will be invited to draw blood approximately 6 months after discontinuation of VKAs. This concerns an additional visit besides the regular care and patients will undergo an extra venipuncture.

Questionnaire

Patients are asked to fill in a questionnaire at home, concerning gender, age, indication for VKA use, length, height, smoking status and history presence of COPD, presence of other pulmonary disease, vitamin D supplementation, use of multivitamins and medication use, whether subjects switch to DOACs or completely discontinue the use of anticoagulants.

Vena punction:

Two non-fasting blood samples of 15mL (EDTA-plasma) and 10mL (EDTA-plasma) will be drawn at baseline. Since patients have regular INR determination at this moment, no extra venipunction has to take place. After six months one non-fasting blood sample of 15mL (EDTA-plasma) will be drawn. At this moment patients will have an additional vena punction. All samples will be collected in the Canisius Wilhelmina Hospital. EDTA-plasma will be centrifuged, divided in two portions of ~1 ml and frozen at -80°C within 2 hours after drawing. One portion will be used for quantification of vitamin K status and one for quantification of the rate of elastin degradation. DNA will be isolated from the samples of 10mL, which will be divided in two portions and frozen at -80°C.

Measurement of plasma desmosine levels:

The rate of elastin degradation will be quantified by measuring plasma (p)DES levels. Subjects with the highest pDES are assumed to have the highest rates of elastin degradation. Isodesmosine and desmosine fractions are measured separately by liquid chromatography-tandem mass spectrometry as previously described using deuteriumlabelled desmosine as internal standard ({ HYPERLINK "http://www.ncbi.nlm.nih.gov/pubmed/?term=17494786" { **HYPERLINK }**: "http://www.ncbi.nlm.nih.gov/pubmed/?term=23727558" }).

Measurement of plasma dp-ucMGP levels:

Plasma dp-ucMGP will be measured using a dual-antibody test based on the previously described sandwich ELISA developed by VitaK (Maastricht, The Netherlands) ({ HYPERLINK "http://www.ncbi.nlm.nih.gov/pubmed/?term=18401181" }). The intra- and interassay variations of this ELISA are 7.6% and 6.8%, respectively, and its sensitivity is 50 pmol/L. Dp-ucMGP levels are very stable for up to fifteen years when frozen at -80°C. The within subject variability of dp-ucMGP is also very limited; in a cohort study little change in dp-ucMGP was observed after 5-6 years.

Determination of VKORC1 polymorphisms

High Pure PCR Template Preparation Kit (Roche Diagnostics, Mannheim, Germany) will be used for isolation of DNA, according to the manufacturer's instructions. For genotyping the

C1173T (rs 9934438) and G-1639A (rs 9923231) single nucleotide polymorphisms of the VKORC1 gene, real-time PCR Fluorescence Resonance Energy Transfer (FRET) analyses will be performed. FRET LightMix® assays (cat.-no 40-0302-16, TIB MOLBIOL, Berlin, Germany) on the LightCycler® (Roche Diagnostics) will be used, according to the manufacturer's protocols. The assay consists of a duplex reaction measuring the melting curves of the used specific fluorescent probes in two different channels, each with a distinct wavelenght. With each run positive (heterozygote, provided with te kit) and negative controles will be determined.

5.3 Withdrawal of individual subjects

Subjects can leave the study at any time for any reason if they wish to do so without any consequences. The investigator can decide to withdraw a subject from the study for urgent medical reasons.

General criteria for withdrawal of individual subjects

- Patients should be withdrawn if VKAs are restarted before all blood samples are drawn.
- Patients should also be withdrawn at any time if the investigator concludes that it would be in the patient's best interest for any reason.
- Patients may voluntarily withdraw from the trial for any reason at any time. They may be considered withdrawn if they state an intention to withdraw, fail to return visits, become lost to follow up for any other reason, or if any of the following occurs: discovery of failure of randomization; discovery of patient ineligibility; errors in treatment compliance; missed/unscheduled/off-schedule/incomplete/incorrect assessments.

If premature withdrawal occurs for any reason, the investigator must determine the primary reason for the patient's premature withdrawal from the trial and record this information in the CRF.

5.4 Replacement of individual subjects after withdrawal

Up to a maximum of 5 subjects who withdraw from the study will be replaced.

5.5 Follow-up of subjects withdrawn from treatment

Patients who prematurely withdraw from the study will be scheduled for an 'end-of-study visit' as soon as possible. At the end of study visit the exact date and the primary reason for withdrawal will be noted in the CRF.

5.6 Premature termination of the study

If failure to enroll sufficient patients occur, premature termination of the study might be warranted. No special actions are needed in case of premature termination of the study. Premature termination of the study will not have any negative implications for the study participants.

6. SAFETY REPORTING

6.1 Temporary halt for reasons of subject safety

In accordance to section 10, subsection 4, of the WMO, the sponsor will suspend the study if there is sufficient ground that continuation of the study will jeopardise subject health or safety. The sponsor will notify the accredited METC without undue delay of a temporary halt including the reason for such an action. The study will be suspended pending a further positive decision by the accredited METC. The investigator will take care that all subjects are kept informed.

6.2 AEs, SAEs and SUSARs

6.2.1 Adverse events (AEs)

Adverse events are defined as any undesirable experience occurring to a subject during the study. All adverse events reported spontaneously by the subject or observed by the investigator or his staff will be recorded.

Participants may experience some discomfort during blood sampling.

6.2.2 Serious adverse events (SAEs)

Since this is an observational study, serious adverse events are not expected and will therefore not be reported.

6.3 Follow-up of adverse events

All AEs will be followed until they have abated, or until a stable situation has been reached. Depending on the event, follow up may require additional tests or medical procedures as indicated, and/or referral to the general physician or a medical specialist.

7. STATISTICAL ANALYSIS

7.1 Primary study parameter(s)

The primary endpoint is the change in plasma desmosine levels. Plasma desmosine levels will be determined at baseline and 6 months after discontinuation of VKAs. Univariate analysis (ANCOVA) will be used for comparing plasma desmosine levels before and after discontinuation of VKAs. Results will be corrected for the following covariates (if statistical significant): age, gender, INR, indication for VKA use, duration of VKA use, BMI, smoking status and history, presence of COPD or other pulmonary disease, vitamin D supplementation, use of multivitamins and use of medication. A *P*<0.05 will be considered statistically significant. Statistics will be performed using SPSS (SPSS Inc., Chicago, Illinois, USA).

Both desmosine and dp-ucMGP levels will be log-transformed before performing statistical analysis.

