7.2 Secondary study parameter(s)

The change in plasma dephosphorylated uncarboxylated matrix Gla-protein at baseline and 6 months after discontinuation of VKAs will be a secondary study parameter. Univariate analysis (ANCOVA) will be used, corrected for the following covariates (if statistical significant): age, gender, INR, indication for VKA use, duration of VKA use, BMI, smoking status and history, presence of COPD or other pulmonary disease, vitamin D supplementation, use of multivitamins and use of medication. Univariate analysis will be used to assess the relationships between dp-ucMGP and desmosine and Pearson's rho will be calculated. To assess the differences of both pDES and d-ucMGP levels between the various VKORC1 polymorphisms, univariate analysis will also be used, corrected for the same covariates as listed above.

Both desmosine and dp-ucMGP levels will be log-transformed before performing statistical analysis.

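### Section 7.1 names a univariate ANCOVA for one group measured twice without stating the pairing; read literally, and with positive within-patient correlation, the primary test is conservative

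*Combined protocol and SAP*

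**What the plan says.** The design is a single group of 30 VKA users with no control arm. Desmosine is measured at baseline and 6 months after stopping (Sections 2, 3 and 5.1.1).

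The endpoint is a within-patient quantity. Section 7.1 opens with "The primary endpoint is the change in plasma desmosine levels", and Section 5.1.1 describes it as "quantified by the change in plasma desmosine levels, measured at baseline and 6 months after discontinuation of VKAs".

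The analysis sentence in 7.1 is worded differently: "Univariate analysis (ANCOVA) will be used for comparing plasma desmosine levels before and after discontinuation of VKAs". It is followed by "Results will be corrected for the following covariates (if statistical significant") and a list of patient characteristics. Baseline desmosine is not on that list. Values are log-transformed and P<0.05 counts as significant.

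Section 7.2 treats dp-ucMGP in the same way: "Univariate analysis (ANCOVA) will be used, corrected for the following covariates (if statistical significant"). For the VKORC1 comparison, "univariate analysis will also be used, corrected for the same covariates as listed above".

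No section names a paired test, a change score as the dependent variable, a patient factor, or a repeated-measures or mixed model. On size, Section 4.4 says: "It concerns a pilot study and therefore sample size calculation was not performed".

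**The concern.** ANCOVA ordinarily compares groups, and here there is only one. An analyst following 7.1 must guess the outcome variable, whether the data have 30 or 60 rows, and which term tests the change. Two readings are natural, and they err in opposite directions.

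- **Literal reading:** level as outcome, time as a factor, 60 rows treated as independent. With a positive within-patient correlation the standard error is too large, and a real fall in desmosine may be missed.
- **Change-score reading:** 30 differences regressed on covariates. The pairing is kept, but choosing covariates by significance shrinks the residual SD by chance, so the test is somewhat too liberal. The text also does not say at which covariate values the mean change is tested.

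The primary P value therefore depends on a model that the plan does not state. With about 30 pairs and no control arm, using each patient as their own control is the main statistical strength of the design.

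**Working it through.** **Inputs.** From the documents: n = 30 patients, two measurements each, log scale, alpha 0.05. Assumed, because the documents do not give them: a two-sided test; correlation ρ of a patient's two log values of 0.3, 0.5, 0.7 or 0.8; complete pairs; normal log values; and a shift that gives the paired t-test 80% power, which is 0.529 SD of the difference. The plan states no power, effect size or SD, so there is no figure of its own to reproduce.

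**Step 1: standard error without covariates.** With SD σ at each time, the literal model assumes variance 2σ²/n for the before/after difference. The true variance is 2σ²(1−ρ)/n. The standard error is therefore too large by 1/√(1−ρ): 1/√0.7 = 1.20, 1/√0.5 = 1.41, 1/√0.3 = 1.83, 1/√0.2 = 2.24.

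**Step 2: true type I error.** The large-sample size is 2(1−Φ(1.96/√(1−ρ))).

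**Step 3: power.** The shift in paired standard errors is 0.529 × √30 = 2.90. Approximate power is Φ(2.90 − 1.96/√(1−ρ)): Φ(0.55), Φ(0.13), Φ(−0.68) and Φ(−1.48), or about 71, 55, 25 and 7%. Simulation agrees closely:

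| ρ | SE ratio | Type I error, formula | Type I error, simulated | Power, simulated |
|---|---|---|---|---|
| 0.3 | 1.20 | 1.9% | 2.0% | 69% |
| 0.5 | 1.41 | 0.56% | 0.69% | 53% |
| 0.7 | 1.83 | 0.04% | 0.07% | 25% |
| 0.8 | 2.24 | 0.001% | 0.01% | 9% |

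The paired t-test had simulated size of about 5% throughout. The direction depends on the sign of ρ: at ρ = −0.3 the literal test would be too liberal (8.6% by formula).

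**Step 4: what the covariates recover.** Section 3 dates the questionnaire: "At baseline, patients are asked to fill in a questionnaire and two additional samples of blood are taken". The Summary records INR at baseline, and no repeat of either is described. Each covariate then has the same value in both of a patient's rows. With complete pairs it cannot alter the before/after estimate; it only removes between-patient variance from the error term.

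This was simulated with 60 rows, 12 continuous candidates (the 7.1 list with COPD and other pulmonary disease counted separately), backward elimination at P<0.05, and 40,000 trials per setting. Three candidates jointly explained a given share of the between-patient variance:

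| Share explained | Power at ρ 0.3 / 0.5 / 0.7 / 0.8 | Type I error at ρ 0.3 / 0.5 / 0.7 / 0.8 |
|---|---|---|
| 0 | 73.5 / 60.9 / 37.3 / 18.6% | 3.0 / 1.1 / 0.3 / 0.06% |
| 30% | 76.2 / 67.2 / 48.0 / 30.1% | 3.5 / 1.9 / 0.5 / 0.2% |
| 60% | 78.2 / 73.2 / 62.0 / 48.9% | 4.2 / 3.1 / 1.4 / 0.6% |

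**Step 5: change-score reading.** This used 30 differences and the same 12 candidates, mean-centred and unrelated to change, with backward elimination and a test of the intercept. Type I error was 6.6 to 7.0%. Across other checks it was 5.7% with a single pass through the full model, 6.3% with one-at-a-time screening, and at most 7.6% under backward or one-at-a-time selection, including with mostly binary covariates.

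**Step 6: which term is tested.** In one simulated data set with two continuous covariates and one 0/1 covariate, the estimated change was −0.2995 in three models: the literal model (SE 0.244), the paired test (SE 0.136), and the change-score model with the 0/1 covariate at its observed share (SE 0.141). With that covariate left at its reference level, the intercept became −0.387 (SE 0.257). The covariate values must therefore be stated.

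**The case against.** The strongest reply is that the plan defines the endpoint as change in several places, so a paired model was probably meant. Section 7.1 names no time factor; the literal model is an interpretation too. This stands in part: what is shown is an unspecified model, and the conservative test follows from one reading of it. It does not rescue the text. The change-score reading brings in the significance screen and leaves the tested quantity undefined. A univariate model with patient as a factor would reproduce the paired test, but covariates that are constant within a patient could not then be estimated alongside it, so the stated correction could not be carried out.

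It is also fair that the correlation, covariate shares, number of candidates and selection rule are all assumed, and that the screen would need attention even if the pairing were stated. The figures are illustrations. For dp-ucMGP, Section 5.2 calls within-subject variability very limited, which points to a positive correlation. That describes a cohort, though, not patients stopping VKAs, and nothing comparable is given for desmosine.

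Finally, this is a pilot without a power target. That limits the severity. But the protocol still sets out a hypothesis and a significance threshold, so the test should be defined.

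**Conclusion.** The concern holds. The plan does not state the pairing or the model behind its primary P value. Under the literal reading with positive within-patient correlation the test is conservative. The loss is small at ρ = 0.3 (power 69 to 78% against 80%) and large at 0.7 (25 to 62%) or 0.8 (9 to 49%), depending on how much the covariates explain. Under a change-score reading with the significance screen, the type I error is roughly 6 to 7.6% instead of 5%. Both are worse than a plain paired analysis.

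These sizes rest on the assumptions listed above, and the actual loss in this study cannot be determined from the documents. The point should be fixed, but it does not invalidate the study.

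**What to change.** In Section 7.1, replace both the ANCOVA sentence and the covariate sentence with text such as:

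> The primary analysis is an unadjusted paired t-test (two-sided, 5%) on the within-patient difference in log desmosine (6 months minus baseline) in patients with both samples, reported as a geometric mean ratio with 95% CI. As a secondary, exploratory analysis, the log difference is regressed on a short pre-specified set of baseline covariates, chosen without a significance screen. Continuous covariates are mean-centred and categorical covariates enter as indicators; the mean change is estimated at the average covariate values and observed category shares.

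Name the set in the text, for example age, gender, smoking status and presence of COPD, all already collected. The sponsor may prefer others from Section 5.1.3; what matters is that the set is short and fixed in advance. Open-ended items (indication, medication) should enter only if grouped beforehand. Another paired model, such as a mixed model with a patient effect, would also serve if it is named.

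In Section 7.2, make the same replacement for the change in dp-ucMGP. Keep the association and VKORC1 sentences, but write the covariates into the VKORC1 sentence, because its cross-reference would otherwise point to a deleted list.

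The cost is wording only: no extra patients or data, and SPSS runs both analyses. The adjusted result becomes secondary. Four pre-specified covariates unrelated to change cost that analysis little: power of 79.6% against 80.0%.
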